#### Post-operative management:

Postoperative surgical visits for suture/staple removal will take place at the JHOC under the current established protocols for seeing patients in person. Masks (patients and clinicians) will be worn at all times, and face shields when appropriate. The same protocol will be followed by the neurology and neuropsychological teams for device activation and initial programming, as well as follow up programming optimization visits, and Tourette Syndrome and neuropsychological rating scales. Similar precautions will be taken for visits related to maintenance of the implanted system, and for implantable pulse generator replacements due to battery depletion.

## 5. Inclusion/Exclusion Criteria

### 5.1. Study Population

The study group will consist of 10 patients with treatment-resistant Tourette Syndrome to undergo DBS of the thalamic Ce-Spv-Voi complex

### 5.2. Inclusion Criteria

1. Males and females who are  $\geq$  15 years of age. There is no strict age cutoff at the upper limit of inclusion, however subjects may meet the exclusion criteria based on medical contraindications to deep brain stimulation surgery (Points 3. and 6. under the **Exclusion Criteria**). For subjects in the age range of 15-24 years, an additional Ethics Committee consultation will be obtained prior to offering the subject the required screening visit. This is based on the revised screening criteria now proposed by Shrock, Mink, et al. on studies investigating DBS in TS (38). Additionally, for subjects in the age range of 15-20, a caregiver will be required to be present for all study visits.
2. Subject has a diagnosis of TS as determined by a review of medical records, discussion with referring psychiatrist as well as the DSM-IV criteria and videotaped assessment. This will include an assessment to determine the presence of psychogenic tics, embellishment, factitious symptoms, personality disorders and malingering.
3. Subject determined to be treatment-resistant for at least one year prior to the Screening Visit as demonstrated by clinical evidence (determined by review of medical records and discussion with referring

Date: 2/24/2021

Principal Investigator: [name], PhD

Application Number: NA\_00073086

psychiatrist or neurologist) of persistent functionally impairing tics that have not responded to treatment with a minimum of three adequate regimens of medication including two failed trials of at least one typical neuroleptic and one atypical neuroleptic medication, along with one failed trial of a first tier medication as defined as follows (standard dosages for these trials are outlined in (1)):

- a. Adequate trials of one non-neuroleptic medication including drugs from the following (first tier) list: clonidine, guanfacine, topiramate, baclofen, levetiracetam, and clonazepam (1). Trial failure is defined as demonstrated lack of efficacy or severe side effects.
- b. Two adequate trials of at least one typical neuroleptic medication (pimozide, fluphenazine, haloperidol) and at least one atypical neuroleptic (risperidone, aripiprazole, ziprasidone, olanzapine, quetiapine). Trial failure is defined as demonstrated lack of efficacy or severe side effects.
4. A mandatory trial of behavioral interventions in an attempt to reduce the severity of the tics or comorbid symptoms must also be completed by the subject before offering participation in this trial. This may include habit reversal therapies, stress reduction therapies, or other behavioral therapies under investigation for tic suppression (36,37).
5. Subject has both significant vocal and motor tics with a tic subscale score of at least 35 on the YGTSS (Yale Global Tic Severity Scale) at all three Baseline Visits prior to undergoing surgery (20). For subjects with predominantly vocal tics (and minimal motor) causing significant problems this score requirement will be reduced to 18, similarly for subjects with predominantly motor tics (and minimal vocal) causing significant problems the required score will be 18 (38). A portion of the study team, including the surgeon and two neurologists, will determine by consensus which category the subject falls into and whether the tics are a significant problem.
6. All other aspects of the subject's care must be optimized during the preceding 6 months before admission to the study. This includes treatment for comorbid medical, neurological, and psychiatric disorders. Additionally, it includes psychological interventions for any ongoing psychosocial problems the subject may have during the preceding 6 months before study admission.
7. Subject must be ambulatory.
8. Females who are postmenopausal, physically incapable of childbearing, or practicing an acceptable method of birth control. Acceptable methods of birth control include surgical sterilization, hormonal contraceptives, or double-barrier methods (condom or diaphragm with a spermicidal agent or intrauterine device [IUD]). If practicing an acceptable method of birth control, a negative urine pregnancy test result has been obtained at baseline Visits 1 and 3.
9. Subject is determined by an independent psychiatrist with expertise in capacity assessments to have decision-making capacity to provide informed consent.
10. Subject is able to read English, understand and cooperate with study procedures, and has signed a written informed consent form prior to any study procedures.

### **5.3. Exclusion Criteria**

Date: 2/24/2021

Principal Investigator: [name], PhD

Application Number: NA\_00073086

1. Subject has a positive urine drug screen at any of the three Baseline Visits.
2. Subject had major surgery within three months prior to Baseline Visit 1 or has other surgery planned during the proposed study period.
3. Subject is determined by medical consultant to have medical contraindications to undergoing surgery.
4. Subject is pregnant or breast-feeding.
5. Subject has a history of alcohol or drug abuse within the past 6 months and/or dependence within the past year.
6. Subject has a medical illness/condition, and/or abnormal diagnostic finding that would interfere with the completion of the study, confound the results of the study, or pose risk to the patient.
7. Subject has an untreated or uncontrolled Axis I disorder or other major psychiatric disorder including major depression, bipolar disorder, or schizophrenia as determined by the screening psychiatrist.
8. Subject has either a current or past history of suicidal plan and/or intent.
9. Subject has a tic disorder or other movement disorder attributable to another medical, neurological, or psychiatric disorder other than Tourette Syndrome.
10. Subject has a drug-induced tic disorder.
11. Subject has significant psychosocial factors that might increase the risk of the DBS procedure or complicate recovery and outcome assessments. (Examples include – history of noncompliance with previous medical and psychosocial treatments, multiple failed medication treatments of inadequate dose or duration, a history of multiple other surgical procedures with poor outcome, unexplained medical history gaps, or pending lawsuits or other legal action.)
12. Subject has metal in the head or any other type of implanted stimulator (i.e. cardiac pacemaker, deep brain stimulator for a different disease, spinal cord stimulator, cochlear implant, vagus nerve stimulator, etc.).
13. Subject has participated in another investigational drug trial or therapeutic trial within 30 days of Baseline Visit 1.
14. Subject has a diagnosis of intellectual disability with documented IQ<70.
15. Subject has a neurological condition, or a history of traumatic brain injury associated with loss of consciousness of > 1 hour and/or intracranial/epidural/subdural bleeding.

## **6. Drugs/ Substances/ Devices**

Deep Brain Stimulation Therapy (DBS) delivers electrical stimulation to areas in the brain and has been approved to help control symptoms of various movement disorders (e.g. DBS of the subthalamic nucleus in

Date: 2/24/2021

Principal Investigator: [name], PhD

Application Number: NA\_00073086

Parkinson's disease or DBS of the thalamus in essential tremor). The surgery for PD or essential tremor patients places electrodes (plastic and metal tubes of diameter 1/16-1/32 inch) in the subthalamic nucleus or ventral intermediate nucleus of the thalamus as identified by radiologic and physiologic criteria. Once the electrodes are implanted, they will be connected to an implanted stimulator plus pulse generator (IPG). The implantable pulse generator powers the electrode. The DBS electrodes, and stimulator pulse generator (one device) are called the System. DBS is not approved for use in Tourette Syndrome. However, the use of DBS has expanded to psychiatric diseases such as treatment-resistant depression and obsessive-compulsive disorder and is currently in early phase studies in other psychiatric disorders.

The primary implantable pulse generators used in this study are derived from the Medtronic Activa deep brain stimulation system, including the PC and RC 2-channel pulse generator models. As of April 1st, 2021, Medtronic will no longer provide the Activa PC for new or replacement implantations, but will support the Percept model implantable pulse generator. New implantations for this protocol in Tourette Syndrome will also only utilize the Percept model pulse generator.

## **7. Study Statistics**

### **7.1. Primary Outcome Variable – Efficacy**

The primary outcome variable will be the clinical response of tic symptoms to treatment, as defined by a 40% decrease from baseline in the Yale Global Tic Severity Scale. The cutoff of 40% was chosen to be consistent with the lower end of improvements observed in previous drug trials treating TS when compared to placebo (1). An improvement in at least one of the three participants is a potential indicator that DBS implantation in treatment refractory Tourette Syndrome can be pursued further.

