### 2. Objectives (include all primary and secondary objectives)

#### 2.1. Primary Objectives

- To evaluate the efficacy of DBS of the thalamic Ce-Spv-Voi complex on tic frequency and severity in 10 subjects with treatment-resistant Tourette Syndrome.
- To evaluate the safety of DBS of the thalamic Ce-Spv-Voi complex in 10 subjects with treatment-resistant Tourette Syndrome.

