## **4. Study Procedures/Overview of Study Design**

### **4.1. Overview of Study Design**

This study is an open-label pilot study to determine the feasibility of DBS of the thalamus (Ce-Spv-Voi complex) in 10 subjects with treatment-resistant Tourette Syndrome (TS). After subjects are determined to have decision-making capacity by an independent psychiatrist or neurologist who is not a member of the study team, they will come in for 3 consecutive baseline visits and will be evaluated by two different study physicians (psychiatrist and/or neurologist) to determine that he/she has a diagnosis of TS. TS symptom scales will be performed at each visit. Subjects who are eligible will undergo a pre-operative diagnostic MRI along with a planning stereotactic planning MRI, and will undergo neurosurgical implantation of the DBS device followed by implantation of a neurostimulator under the chest wall. Subjects will be monitored at Weeks 1, 2, 3, 4 and then at Months 3, 6, 9 and 12 after implantation of the neurostimulator. At each visit, subjects will be assessed for adverse events and will undergo routine procedures for monitoring patients who undergo DBS, including recording concomitant medications, optimization of stimulation parameters, TS symptom scale assessments to document changes in symptoms, and neuropsychological assessment to document any changes in cognition. No blinding will be performed. Subjects will continue their pre-surgical psychiatric medications and any changes in medications will be documented at each study visit.

The subjects will be followed for one year after implantation. We estimate three implantations per year will be performed, implying just over three years required to complete the implantations. We estimate the full

Date: 2/24/2021

Principal Investigator: [name], PhD

Application Number: NA\_00073086

study duration to be 5-6 years to complete the initial 13 Visits for all of the subjects, prior to the long-term follow-up segment of the study which involves visits approximately semiannually for 2 years followed by annually for the duration of device implantation.

Because this study is being conducted on a vulnerable clinical population, an independent psychiatrist that is not a member of the investigational study team with experience in capacity assessments will assess the decision-making capacity of each potential subject prior to any study-related activities.

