#### **4.8. Visits 6 – 9 – Follow-up/Optimization of Programming**

These visits begin approximately 3 weeks after Visit #5.

A study neurologist (with experience in programming DBS devices who has extensive experience working with patients with movement disorders undergoing DBS) in conjunction with one of the study psychiatrists will set initial stimulation parameters. As this procedure is experimental, the stimulation parameters will be modified empirically and individualized for each subject. However, attempts will be made to use typical clinical ranges for DBS of the thalamus (electrode voltage 1 – 5.0 V, pulse width 60-210 microseconds, and stimulation frequency 130 – 185 Hz (35). These numbers indicate the ranges and maxima for the stimulation parameters to be used in this protocol. These represent conservative values with respect to the safety of the stimulation, as indicated by the limits incorporated into the Medtronic programmer. The study neurologist experienced in programming in conjunction with one of the study psychiatrists will use TS symptom scales (especially the Severity Ratings section of the YGTSS, incorporating measures of tic frequency and intensity) to optimize the DBS programming at all subsequent follow-up visits. In situations of partial response as assessed over the previous week, the stimulation voltage intensity may be increased,

Date: 2/24/2021

Principal Investigator: [name], PhD

Application Number: NA\_00073086

or the frequency and pulse width settings modified within the limits stated above to seek a more complete response. Any acute changes in OCD or ADHD symptoms, acute changes in depression or anxiety symptoms, and/or appearance of adverse events deemed likely to be related to DBS programming may prompt a reduction in stimulation voltage, change in stimulation contacts used, or alteration in frequency or pulse width.

At the time of initial programming, the subjects will receive additional literature as well as the appropriate patient controller device, which allows them to turn the stimulation on or off. The subjects will be instructed in its use and receive pocket cards and materials to carry with them.

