#### 4.12. Table of Visits and Testing

Visit #	Approx. Week #	TS symptom scales	Other psych testing	Surgical procedures	Adverse event monitoring	IPG programming	Medication change monitoring	Urine tox
1	0	DSM-IV SCID, YGTSS,YBOCS, WHO ASRS	Ham-D, BAI,GAF, CSSS,YMRS,NCOG	NA	NA	NA	medications recorded	yes
2	2	DSM-IV SCID, YGTSS,YBOCS, WHO ASRS	Ham-D, BAI,GAF, YMRS	NA	NA	NA	yes	yes
3	4	YGTSS,YBOCS, WHO ASRS	Ham-D, BAI, CSSS,YMRS	NA	NA	NA	yes	yes
4	7	NA	NA	Implantation of DBS leads	yes	NA	NA	NA
5	8	YGTSS,YBOCS, WHO ASRS	Ham-D, BAI, YMRS	Implantation of IPG	yes	yes	yes	NA
6	11	YGTSS,YBOCS, WHO ASRS	Ham-D, BAI,GAF, CSSS,YMRS,NCOG	NA	yes	yes	yes	NA
7	12	YGTSS,YBOCS, WHO ASRS	Ham-D, BAI,GAF, YMRS,NCOG	NA	yes	yes	yes	NA
8	13	YGTSS,YBOCS, ADHD	Ham-D, BAI,GAF, CSSS,YMRS,NCOG	NA	yes	yes	yes	NA
9	14	YGTSS,YBOCS, WHO ASRS	Ham-D, BAI,GAF, YMRS,NCOG	NA	yes	yes	yes	NA
10	23	YGTSS,YBOCS, WHO ASRS	Ham-D, BAI,GAF, CSSS,YMRS	NA	yes	yes	yes	NA
11	35	YGTSS,YBOCS, WHO ASRS	Ham-D, BAI,GAF, YMRS,NCOG	NA	yes	yes	yes	NA
12	47	YGTSS,YBOCS, WHO ASRS	Ham-D, BAI,GAF, CSSS,YMRS	NA	yes	yes	yes	NA
13	62	YGTSS,YBOCS, WHO ASRS	Ham-D, BAI,GAF, YMRS,NCOG	NA	yes	yes	yes	NA

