### **7.2. Secondary Outcome Variables – Efficacy**

Secondary efficacy variables will include mean change from baseline scores of the YBOCS and WHO Adult ADHD Self-Report Scale inventories. Response as defined by a 20% decrease from baseline will also be calculated.

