### **7.4. Statistical Plan**

This is a pilot study looking at using DBS in 10 Tourette Syndrome patients.

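### Section 7.1 states its go-forward criterion for three participants in a 10-subject study, and plans no mean change in the YGTSS beside the 40% responder count

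*Combined protocol and SAP*

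**What the plan says.** The first primary objective (section 2.1) is "To evaluate the efficacy of DBS of the thalamic Ce-Spv-Voi complex on tic frequency and severity" in 10 subjects. Section 7.1 turns this into a yes/no outcome: "The primary outcome variable will be the clinical response of tic symptoms to treatment, as defined by a 40% decrease from baseline" in the YGTSS. It closes with the only interpretive criterion for efficacy in the plan: "An improvement in at least one of the three participants is a potential indicator" that this use of DBS can be pursued further.

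Section 7.2 reads "Secondary efficacy variables will include mean change from baseline scores of the YBOCS and WHO Adult ADHD Self-Report Scale inventories", and adds a 20% responder cut for them. Section 7.4, the statistical plan, is one sentence: "This is a pilot study looking at using DBS in 10 Tourette Syndrome patients". No section plans a mean change in the YGTSS.

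Section 7.1 does not name the visit, the YGTSS score or the baseline rule. The YGTSS is scored at three pre-operative visits, at Visit 5 and at Visits 6 to 13 (section 4.12). Entry (section 5.2, item 5) uses the tic subscale. On design, section 4.1 says "No blinding will be performed".

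**The concern.** There are two faults.

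First, the go-forward sentence is written for a group of three that does not exist in this study. Sections 1, 2.1, 2.2, 4.1, 5.1, 7.4 and 7.5 all say 10. Three is also the estimated number of implantations per year (section 4.1) and the count that stops the study (section 7.5), but nothing links section 7.1 to either. The sentence also leaves improvement undefined. Section 4.11 speaks of no improvement on the YGTSS, for treatment failure, with no threshold, so the protocol itself uses the word apart from the 40% cut. A criterion of one in three is not the same as one in 10, and the plan does not say which it will apply.

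Second, the primary scale gets a thinner analysis than the secondary ones. The YBOCS and the ASRS each get a mean change and a responder cut; the YGTSS gets only the cut. The size of the tic change, which is what a pilot would hand on to a later trial, is not a planned result.

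**Working it through.** The plan states no power, alpha or null response rate, so there is no figure of its own to reproduce.

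**Step 1: the criterion with 3 and with 10 subjects.** Inputs: n = 3 (section 7.1), n = 10 (section 7.4), and a true response rate p, which the documents do not give; I show 5% to 40%. The chance of at least one responder is 1 − (1 − p)^n. For p = 10%: 1 − 0.9^3 = 0.271 and 1 − 0.9^10 = 0.651. For comparison, at least two of 10 is 1 − (1 − p)^10 − 10p(1 − p)^9; at p = 10% this is 1 − 0.349 − 0.387 = 0.264. At least three of 10 is the corresponding binomial tail.

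| True response rate (assumed) | ≥1 of 3 | ≥1 of 10 | ≥2 of 10 | ≥3 of 10 |
|---|---|---|---|---|
| 5% | 0.14 | 0.40 | 0.09 | 0.01 |
| 10% | 0.27 | 0.65 | 0.26 | 0.07 |
| 20% | 0.49 | 0.89 | 0.62 | 0.32 |
| 40% | 0.78 | 0.99 | 0.95 | 0.83 |

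Carrying 'at least one' over to 10 raises the chance of a positive signal at low response rates by a factor of more than two. The smallest result that meets the criterion also says little: 1 of 3 has an exact 95% CI of 0.8% to 90.6%, and 1 of 10 of 0.3% to 44.5%.

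**Step 2: what a count leaves out.** Take 4 responders of 10 as an example. Clopper-Pearson 95% CI: 12.2% to 73.8%. Two sets of individual falls that both give this count:

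- four at 40% and six at 0%: (4×40 + 6×0)/10 = 16%
- four at 80% and six at 39%: (4×80 + 6×39)/10 = 55.4%

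These are illustrations, not limits. The earlier result at this target cited in section 3.2 is a 37% YGTSS difference, just below the 40% cut. It compares stimulation on with off, so it is not directly comparable with change from baseline.

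**Step 3: what a mean would give.** The 95% half-width is t(0.975, 9 df) × SD/√10, with t = 2.262. The SD of percent change is not in the documents. Assumed SDs of 20, 25 and 35 points give half-widths of 14.3, 17.9 and 25.0 points. That is also wide, but it states a size.

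**The case against.** This is an open-label feasibility pilot with no hypothesis test, so missing alpha and power are not errors and a responder endpoint is legitimate. The sentence in section 7.1 speaks only of a potential indicator, not a decision rule, and 'three' may be leftover text. The list in section 7.2 need not be exhaustive. YGTSS scores are recorded at nearly every visit, so the size of change could be worked out later. All of this is fair. It means the mean change is unplanned rather than lost, and that the first fault is cured by an edit. It does not remove the conflict between three and 10, and simply replacing the number would more than double the chance of a positive signal at a 10% rate.

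Three stronger readings are tempting, and the documents do not support them.

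- A reader might infer that any fall in score counts as improvement, so that the criterion is almost sure to be met. The sentence follows directly on the 40% definition and its justification, so the 40% response is the natural reading. Section 4.11 leaves a doubt worth closing, no more.
- A reader might infer that response at any visit counts, inflating the number of responders. No section says so. Visit 13, the 12-month study completion visit, is the natural reading. Any figure for inflation would rest on a visit-to-visit SD that the documents do not give.
- A reader might infer that the open score and baseline leave the outcome without meaning. Section 7.1 names the scale, and the programming guidance ("especially the Severity Ratings section of the YGTSS, incorporating measures of tic frequency and intensity") is an aid to setting the device, not a rival outcome. The three pre-operative visits are called baseline visits. A borderline subject could change status: a follow-up score of 25 is a fall of 28.6%, 37.5% or 44.4% from baselines of 35, 40 or 45. That justifies a clause, but is not evidence of a distorted count.

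**Conclusion.** The point holds in two parts. The go-forward sentence contradicts the study size and leaves its key word undefined. Moving from 3 to 10 subjects changes the chance of meeting it from 27% to 65% at an assumed 10% response rate, and from 14% to 40% at 5%. The primary scale is the only efficacy scale without a planned mean change, and a count alone cannot tell a small average effect from a large one. The binomial figures rest only on the assumed response rate and independent subjects; the half-widths rest on an assumed SD of 20 to 35 points and a t interval.

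This should be corrected but does not invalidate the study. The unnamed visit, score and baseline are details to settle in the same edit, not separate harms.

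**What to change.** 1. Restate the last sentence of section 7.1 for the 10 subjects and say that improvement means the 40% response. Reconsider 'at least one': in 10 subjects, at least two gives 26% at a 10% response rate, close to the 27% of one in three, and at least three gives 7%. The choice is the sponsor's, made before analysis.
2. Add mean percent change in the YGTSS from the pre-operative baseline to the 12-month Visit 13, with a 95% CI and the number of subjects contributing, and list each subject's scores. Report beside it the responder proportion out of all implanted subjects with an exact 95% CI.
3. In the same edit, name the visit (Visit 13 is the natural reading), the YGTSS score (total or tic subscale, the sponsor's choice) and the baseline rule, for example the mean of Visits 1 to 3. Section 4.10 also uses Visit 13 for early termination, so say how a score taken then is shown.

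The cost is protocol wording and one extra summary of data already collected. The mean will have a wide interval, about 14 to 25 points either side under the assumed SDs, and a higher threshold would make a positive signal harder to reach. None of this separates a stimulation effect from non-specific improvement, because the study has no control and no blinding.

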### 3. Background

DBS has been used successfully for the treatment of patients with treatment-resistant movement disorders such as Parkinson's Disease (PD) (14), tremor (15) and dystonia (16). Stimulation of electrodes implanted in deep brain structures modulates activity in brain circuits leading to symptom improvement. More recently, DBS has been proposed as a therapeutic alternative for patients with treatment-resistant depression after scientists observed that the subgenual cingulate region (Brodmann area 25) is overactive in patients with depression refractory to traditional treatments such as antidepressants and electroconvulsive therapy (17). DBS is unique among neurosurgical techniques in that it can easily be studied in a placebo-controlled study design; patients can serve as their own controls in crossover designs in which the stimulator is turned on or off in a blinded fashion. Controlled trials of DBS in depression are currently ongoing. Additional benefits of DBS include that unlike ablative surgery, DBS is reversible and produces little to no tissue damage (18). Because of these advantages, investigators at Johns Hopkins plan to develop a protocol for DBS to target tics in patients with treatment-resistant Tourette Syndrome (defined as patients with persistent tics that have not responded to front-line medical agents such as clonidine, guanfacine, or topiramate). In addition, the intended DBS target may also affect other concurrent psychopathologies such as ADHD or OCD (1).

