### **3.2 Initial Stimulation Data**

Early clinical reports on the effectiveness of DBS for TS included those of the Dutch Flemish Tourette Surgery Study Group (2, 5) with bilateral thalamic stimulation, as well as a case of bilateral GPi stimulation for refractory TS by Diederich et al. (3). In these two reports, there were substantial reductions in the numbers and frequencies of tics and compulsive behavior (2, 3). Additionally, Flaherty et al. recently published a case of a patient with TS undergoing bilateral anterior internal capsule DBS placement (with the last electrode in the nucleus accumbens.) At 18 months of follow-up the patient demonstrated significant reductions in tic frequency and severity as well (4). A series of 5 patients with TS were examined in a double-blind fashion by Maciunas et al. after undergoing bilateral DBS placement at the Visser-Vandewalle target in the medial and ventral thalamus (31). Four stimulation states were examined in a blinded fashion, including either unilateral stimulation, both on, or no stimulation. The bilateral stimulation state showed statistical improvements in motor and vocal tic numbers and other TS symptom inventories, with 3/5 patients exhibiting marked improvement (31). Additionally, Servello et al. reported on 18 patients undergoing bilateral thalamic stimulation in the same target for refractory TS. These patients demonstrated significant improvements as well up to 18 months of follow-up (32). And more recent positive results were obtained by Ackermans et al. using the thalamic Ce-Spv-Voi complex target in a small double-blind trial involving six patients (6). This group demonstrated a 37% improvement in the Yale Global Tic Severity Scale between DBS on and off states.

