#### **4.7. Visit 5 – Implantation of the Neurostimulator**

Approximately 1 week after Visit #4.

Approximately one week after the subject is discharged from the hospital from the neurosurgical implantation, the subject will return for implantation of the neurostimulator under the chest wall. The intracranial electrode will be connected to the neurostimulator plus battery that powers the electrode.

The following assessments will be conducted:

- New/changed adverse events
- Record changes in concomitant medications
- TS and associated condition symptom scales (YGTSS, YBOCS, and the WHO ASRS). Repeat Ham-D, BAI, and YMRS for depression, anxiety, and /or mania symptoms. For ages 15-17, the Ham-D and BAI scales will be replaced with the Beck Youth Inventory.
- Schedule post-operative diagnostic MRI of the brain (to assess lead placement prior to implantable pulse generator programming). A head CT will be obtained if there are MRI contraindications.

At the conclusion of this visit, the subject will be given an appointment card for the next study visit.

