### **7.5. Early Stopping Rules**

Date: 2/24/2021

Principal Investigator: [name], PhD

Application Number: NA\_00073086

DBS will be discontinued if the subject experiences a worsening of his tic or other Tourette symptoms (or OCD, ADHD, depression, or anxiety symptoms) without returning to baseline (prior to DBS implantation) within 4 weeks from the worsening of the symptoms. DBS will be discontinued if subjects experience suicidal ideation or mania that does not improve with turning off the stimulator. DBS will also be discontinued if neurologic symptoms including muscle contractions, flashing lights, electric jolting sensations, increase in dyskinesias will not improve with stimulator setting change and they are severe enough to interfere with patient daily functioning. Finally DBS will be discontinued if subjects are unable to tolerate the stimulator for any reason not foreseen by the investigator and that clearly interferes with subject's functioning.

Subjects will also be removed from the study for any significant adverse events that jeopardize patient safety. This includes any events related to the surgical procedure or subsequent DBS stimulation therapy. The entire study of 10 subjects will be stopped should the number of subjects meeting the above **Early Stopping Rules** reaches 3 at any point in the study. If this occurs before the full subject recruitment goal has been met, no further subjects will be recruited.

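### Section 7.1 measures response only from the pre-surgical baseline; YGTSS scores that appear to fall after lead placement and before first activation are collected but not used

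*Combined protocol and SAP*

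**What the plan says.** The first primary objective in Section 2.1 is "To evaluate the efficacy of DBS of the thalamic Ce-Spv-Voi complex on tic frequency and severity". Section 7.1 makes the primary outcome a clinical response "as defined by a 40% decrease from baseline in the Yale Global Tic Severity Scale" and says the cutoff was chosen to be "consistent with the lower end of improvements observed in previous drug trials treating TS when compared to placebo". It then gives a decision rule: "An improvement in at least one of the three participants is a potential indicator that DBS implantation" can be taken further.

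Section 7.1 does not define baseline. The stopping rules do, in passing: "without returning to baseline (prior to DBS implantation) within 4 weeks from the worsening of the symptoms". Visits 1 to 3, all before surgery, are the ones called Baseline Visits.

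Section 4.7 has these scales collected at Visit 5: "TS and associated condition symptom scales (YGTSS, YBOCS, and the WHO ASRS". Section 4.8 repeats YGTSS at Visit 6, which it identifies as the initial programming session. Sections 7.1, 7.2 and 7.4 give neither score a role. Section 4.1 states that there is no blinding, and no control arm or off-stimulation period is planned.

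**The concern.** The objective concerns the efficacy of DBS, and Section 3 explains DBS as stimulation acting on brain circuits. The outcome is the difference between a score before surgery and a score on stimulation. Several things other than stimulation can move it:

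- **Lead placement.** Section 3.1 reports tic improvement after deliberate lesions in the same three structures. Section 3 says DBS does little tissue damage, so this makes a placement effect plausible but says nothing about its size.
- **Expectation**, after brain surgery in an unblinded trial.
- **Regression to the mean.** Section 5.2 requires a qualifying tic score at all three baseline visits, so entry selects on high scores.

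A subject who improved before the device was ever switched on would be counted in the same way as one who improved on stimulation, and nothing in the planned reporting would show the difference. The protocol recognises the underlying idea, since Section 3 notes that "patients can serve as their own controls in crossover designs in which the stimulator is turned on or off in a blinded fashion". This trial does not use that design. A score taken after surgery and before activation would be the only planned within-trial reference for a subject who has had surgery and not yet had stimulation.

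**Working it through.** The plan gives no sample-size derivation, assumed response rate, standard deviation or test, so there is no figure to reproduce. The check compares the passages and then works an illustration.

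**1. Timing, from Table 4.12.** Leads are placed at Week 7 (Visit 4), the neurostimulator is implanted at Week 8 (Visit 5), Visit 6 is at Week 11 and Visit 13 at Week 62. Visit 5 is therefore 8 − 7 = 1 week after lead placement, and Visit 6 is 11 − 7 = 4 weeks after. From Visit 6 to the final visit is 62 − 11 = 51 weeks.

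**2. Are these scores off stimulation?** Sections 4.7 and 4.8 put post-operative imaging before programming and the initial programming at Visit 6. On that reading Visit 5 is off stimulation, and Visit 6 is too if the rating comes before programming; the order is not stated. Table 4.12, however, marks IPG programming at Visit 5. Section 4.1 describes monitoring from Week 1 after neurostimulator implantation, with parameter optimisation at each visit. If programming starts at Visit 5, the Visit 6 score is on stimulation and only a Visit 5 score rated before programming could serve.

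**3. How much an unseen early change could matter.** Let d be the proportional fall from baseline before activation. A responder needs a final score of at most 0.60 × baseline, so the further proportional fall needed from the pre-activation score is

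1 − 0.60 / (1 − d).

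With a baseline of 35 (the general entry minimum in Section 5.2), the responder cut is 0.60 × 35 = 21. The values of d are assumptions.

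| d | Pre-activation score | Further points needed | Further fall needed |
|---|---|---|---|
| 0% | 35.0 | 14.0 | 40.0% |
| 10% | 31.5 | 10.5 | 33.3% |
| 20% | 28.0 | 7.0 | 25.0% |
| 30% | 24.5 | 3.5 | 14.3% |
| 40% | 21.0 | 0 | 0% |

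**4. The decision rule.** If a fraction p of subjects reached the cutoff with no stimulation effect, the chance of at least one responder among n is 1 − (1 − p)^n. Section 7.1 says three participants while ten are planned, so both are shown; p is again assumed.

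| p | n = 3 | n = 10 |
|---|---|---|
| 5% | 14.3% | 40.1% |
| 10% | 27.1% | 65.1% |
| 20% | 48.8% | 89.3% |

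**5. What a split can and cannot show.** Take the d = 20% row with a final score of 21. The fall of 14 points divides into 7 before activation and 7 after, and the second part is 7/28 = 25%. If the early 7 points would have faded by the final visit without stimulation, the score off stimulation at that time would be 35 and the stimulation effect 14 points (40%). The split would then report half of it. The second part is therefore a description, not an estimate of the stimulation effect.

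**The case against.** The strongest reply is that the plan does not claim what it cannot show. Section 7.1 speaks of response to treatment, and its decision is about pursuing implantation. Section 4.1 calls the study an open-label feasibility pilot. For a decision about the whole procedure, change from before surgery is a reasonable measure. This stands: the documents do not say that the response will be attributed to stimulation alone. A reader might infer it from the efficacy objective and Section 3, but it remains an inference.

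A reader might also infer that the response will be set against the result in Section 3.2, "This group demonstrated a 37% improvement in the Yale Global Tic Severity Scale between DBS on and off states". No passage plans that comparison. The 37% appears only as background, and the reference to drug trials explains why 40% was chosen. Nor would the change after activation be a fair match for the 37%: it is open-label, sequential, spread over about 51 weeks from Visit 6, and exposed to medication changes, whereas the cited trial was double-blind.

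The schedule objection also stands. Because Table 4.12 and Sections 4.7 and 4.8 disagree, it cannot be assumed that Visit 6 is off stimulation.

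None of this removes the remaining point: scores that may show a change before activation are collected, and the plan has no place for them.

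**Conclusion.** The concern holds in a limited form. The primary outcome cannot distinguish change before activation from change after it, and the plan leaves unused the scores that could show the difference in part. This is an inexpensive improvement to interpretation; it does not invalidate the 40% endpoint.

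The conclusion rests on reading baseline as pre-surgical, which comes from Section 7.5 and the visit names because Section 7.1 is silent. It also rests on there being at least one YGTSS score before first activation, which Sections 4.7 and 4.8 imply and Table 4.12 puts in doubt.

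The size is unknown. The documents report no surgery-only change, so the 33%, 25% and 14% figures and the decision-rule probabilities show only what would follow from the assumed values. They are not evidence that such a change will occur.

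**What to change.** 1. Reconcile Table 4.12 with Sections 4.7 and 4.8 (and with the outline in Section 4.1) on when programming starts.
2. Require YGTSS to be completed before the stimulator is first switched on, at whichever visit that proves to be.
3. Keep the 40% response from pre-surgical baseline as the primary outcome. Add to Section 7.1 a descriptive report, for each subject and as a mean, of the YGTSS change from baseline to the last pre-activation score, and from that score to the final visit.
4. State that response from baseline reflects the whole DBS procedure and is not a placebo-controlled effect, and that the placebo-compared drug figures serve only to explain the cutoff.
5. Do not present the change after activation as equivalent to the 37% on/off result.

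The cost is a few sentences in Section 7.1 and one ordering instruction, with no new visit or scale. The change after activation may look smaller than the total. The split leaves expectation at activation and medication changes in place, and it understates the stimulation effect if an early post-operative improvement would have faded by the final visit. The report should state these limits.
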